6.3.3.1 Treatment-Emergent AE (TEAE)

An adverse event is considered treatment-emergent if it occurs after digoxin and/or bexagliflozin administration and if the date –time or date of onset is on or after the date of first dose of study medication, or worsens during the treatment period (intensity/severity grades worsen).

6.3.3.2 Serious Adverse Events (SAE)

AEs will be categorized as serious or non-serious using the definition specified in Section 6.9 of the study protocol.

6.3.3.3 Immediately Reportable AE (IRAE)

An IRAE is any serious adverse event or any adverse event that necessitates discontinuation of the study drug.

6.3.3.4 Adverse Events Counting Rules

1. A subject with more than one different AE in a particular system organ class (SOC) will be counted only once in the total of subjects experiencing adverse events in that particular SOC.
2. A subject having experienced the same event (AE preferred term) more than once during the study will be counted only once in the number of subjects with that event.
3. A subject having experienced the same event (AE preferred term) more than once during the study with a different severity or seriousness, it will be counted only once with the worst grade and seriousness respectively.
4. A subject having experienced the same event (AE preferred term) more than once during the study with a different causal relationship to the study drug, it will be counted only once by considering the most-related documented degree of relationship.

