2.2 Secondary Objectives

The secondary objective of this study is to evaluate the safety and tolerability of digoxin when co-administered with bexagliflozin.

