6.3.3 Adverse Events (AEs)

Adverse events will be collected and coded using version 20.1 Sept 2017 (or newer) of MedDRA. Analysis of adverse events will be carried out on the Safety Population. All adverse events will be included in the individual subject data listings. Only treatment emergent adverse events (TEAEs) will be tabulated in summary tables. The incidence of TEAEs will be presented by treatment. If the AE(s) onset date-time or date occurs after the first dose up until right before the first dose in the second treatment period, the AE(s) will be assigned to the first treatment period. If the AE(s) onset date-time or date occurs after the first dose in the second treatment period, the AE(s) will be assigned to the second treatment period. A similar approach will be used with respect to all subsequent treatments.

All adverse events will be assessed by the investigator(s) with respect to severity, relationship to study drug and seriousness.

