8.4.1 Adverse Events

All AEs will be coded to system organ class (SOC), and preferred term (PT), using the latest Medical Dictionary for Regulatory Activities coding dictionary (version to be specified in the clinical study report). All reported AEs will be listed, but only TEAEs will be summarized.

The incidence of all TEAEs will be summarized by treatment. In the summary tables, subjects may be counted under multiple SOCs and PTs, but for each SOC and PT, subjects are only counted once. If a subject has the same AE on multiple occasions, the highest severity (severe > moderate > mild) or drug relationship (definite > probable > possible > not likely related > unrelated) recorded for the event will be presented. If severity is missing, subjects will be included as missing (for severity). If drug relationship is missing, subjects will be included in related tables (e.g., considered related). Summary tables will be organized by SOC, then PT.

The following summaries will be presented for TEAEs:

- Overall Summary of TEAEs by Treatment
- Incidence of TEAEs by Treatment, System Organ Class, and Preferred Term
- Incidence of Treatment Emergent Serious Adverse Events by Treatment, System Organ Class, and Preferred Term

Subjects who prematurely discontinued due to TEAEs and subjects with serious TEAEs will be listed.

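### The SAP counts a repeated adverse event term once per study, but its tables are by treatment in a crossover; the counting rules should apply within each treatment (minor)

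*SAP*

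**What the plan says.** SAP 6.3.3.4 gives four counting rules. Rule 1 counts a subject once per system organ class and names no time span. Rules 2 to 4 deal with a preferred term that recurs, and each takes the whole study as its span:

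- Rule 2: such a subject with the term "more than once during the study will be counted only once in the number of subjects with that event".
- Rule 3, where severity or seriousness differs between occurrences: "it will be counted only once with the worst grade and seriousness respectively".
- Rule 4, where causality differs: "it will be counted only once by considering the most-related documented degree of relationship".

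The displays are by treatment. SAP 6.3.3 says "The incidence of TEAEs will be presented by treatment" and assigns each event to a treatment period by its onset. An event that "occurs after the first dose up until right before the first dose in the second treatment period" belongs to the first period, and later onsets belong to the second. SAP 8.4.1 says "The incidence of all TEAEs will be summarized by treatment" and lists three summaries: an overall one, incidence by system organ class and preferred term, and serious events.

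SAP 8.4.1 also restates the counting rules. A subject counts once per class and per term, and "If a subject has the same AE on multiple occasions, the highest severity" (or the strongest drug relationship) is shown. Neither sentence is limited to a treatment. Protocol 9.6.1 adds tabulations by severity and by relationship to bexagliflozin.

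**The concern.** A rule that counts a subject once per study suits a parallel-group trial, where each subject sits in one column. Here each subject is due to contribute to both. A subject with headache under Treatment A and again under Treatment B has one permitted count and two columns to fill. The SAP does not say whether the first occurrence, the last, the worst or some other occurrence decides. Whatever is chosen, one column omits a subject who had the event on that treatment.

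Grade and causality raise the same problem. If the subject is kept in both columns but rules 3 and 4 are applied over the whole study, a moderate event under one treatment would be shown as moderate under the other, where it was mild.

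The by-treatment tables are part of the evidence for the secondary objective, to "evaluate the safety and tolerability of digoxin when co-administered with bexagliflozin". With 18 subjects, moving a single subject is visible in a percentage.

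**Working it through.** The documents give no adverse event rate and no derived figure to reproduce. The check is therefore a reading of the text followed by an illustration under stated assumptions.

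**Text.** The steps the SAP asks for are:

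1. Assign each event to a treatment period by onset (SAP 6.3.3).
2. Collapse repeats of a preferred term to one per subject across the study (SAP 6.3.3.4, rules 2-4).
3. Tabulate by treatment (SAP 6.3.3 and 8.4.1).

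Step 2 removes the distinction that step 1 makes and step 3 needs. No sentence in SAP 6.3.3, 6.3.3.4 or 8.4.1 limits step 2 to a treatment or says where a collapsed repeat goes.

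**Worked example (invented counts).** Take 18 subjects: 3 with a term under both treatments, 2 under A only and 1 under B only.

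- Counting within each treatment: A = 5/18 = 27.8%; B = 4/18 = 22.2%; 9 subject-counts in all.
- Counting once per study: 3 + 2 + 1 = 6 subject-counts.
- If the 3 repeats all go to A: A = 5/18 = 27.8%, B = 1/18 = 5.6%.
- If they all go to B: A = 2/18 = 11.1%, B = 4/18 = 22.2%.

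The same data can therefore favour either treatment, depending on a rule that the SAP does not state.

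**Expected size when there is no treatment effect.** Inputs:

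- N = 18, allocated 1:1 (SAP 3.2).
- Assumed: incidence p of the term is the same on both treatments, 10% or 20%.
- Assumed: within-subject correlation r between having the term on A and on B, 0 or 0.5.

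Formulas:

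- Share with the term on both = p² + r·p·(1 − p). For p = 0.20 and r = 0.5 this is 0.04 + 0.5 × 0.16 = 0.12.
- Expected subjects with it on both = 18 × that share.
- Even split of repeats: each column falls to p − share/2.
- All repeats to one treatment: the other column falls to p − share, and the first stays at p.

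| p | r | Share on both | Subjects of 18 | Each column, even split | Reduced column, all repeats to the other |
|---|---|---|---|---|---|
| 10% | 0 | 0.010 | 0.18 | 9.5% | 9.0% |
| 10% | 0.5 | 0.055 | 0.99 | 7.25% | 4.5% |
| 20% | 0 | 0.040 | 0.72 | 18.0% | 16.0% |
| 20% | 0.5 | 0.120 | 2.16 | 14.0% | 8.0% |

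With an even split the expected difference between columns is zero in every row. With all repeats in one column the apparent difference equals the share: 1.0, 5.5, 4.0 and 12.0 points.

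**The case against.** The best defence is that nobody would program the rules study-wide. SAP 6.3.3 assigns events to periods first, the incidence table is by treatment, class and term, and SAP 5.1 analyses subjects according to the treatment received. Taken together, a programmer would probably count once per term within each column. The table shells are a companion document (SAP 1 and Appendix 4), not available here, and may already do this. That stands: the documents show a defective rule, not a defective table. It does not remove the need to correct the wording, because rules 2-4 name the study as their span and SAP 8.4.1 does not narrow it.

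Rules 3 and 4 also have limited reach. None of the three summaries listed in SAP 8.4.1 is by severity or relationship; those tabulations come from Protocol 9.6.1. This stands too, although SAP 8.4.1 does say how missing severity and relationship are handled, so some display of them is expected.

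Two stronger readings are tempting, and neither is supported.

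- A reader might infer that the tables will show a false treatment difference of up to 12 points. That needs every repeat to go to the same treatment, which the documents nowhere say. Keeping the first or last occurrence sends repeats to A in one sequence and to B in the other, with 1:1 allocation. Keeping the worst grade favours neither treatment when there is no effect. Under such rules both columns shrink together.
- A reader might infer that onsets on the bexagliflozin-only days before digoxin (Days 1-2 in Group 1, Days 15-16 in Group 2) are wrongly placed under Treatment A. They are not. SAP 1 defines Treatment A as the whole 8-day bexagliflozin course with digoxin on its third day. A separate display of those days would be a preference. The onsets can be picked out of the listings, because digoxin is given on fixed days.

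**Conclusion.** The concern holds as a conflict in the text. The counting span in SAP 6.3.3.4 rules 2-4 does not fit the by-treatment tables of a crossover, and SAP 8.4.1 repeats the rules without correcting them. The reading is firm; whether any table will be affected is not known, because the shells may already count per column.

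The severity is minor. The likely effect, if the rule is followed and repeats fall evenly, is that both columns are understated by 0.5 to 6 points for a term with 10-20% incidence, with no expected bias between treatments. The incidences and correlations are assumptions. No formal hypothesis test is planned (SAP 3.3), every event is listed, and the pharmacokinetic analysis does not depend on these rules.

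**What to change.** - SAP 6.3.3.4, rules 2-4: replace *during the study* with *within each treatment*.
- SAP 6.3.3.4, rule 1: add *within each treatment*.
- SAP 8.4.1: add the same words to the sentence counting a subject once per class and term, and to the sentence on highest severity or relationship.
- If any table has an overall column, state that study-wide counting applies to that column only. A footnote should say that the treatment columns need not add up to it, since a subject may appear in both.
- Check that the table shells follow the same rule, including any severity or relationship tabulation made under Protocol 9.6.1.

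The cost is a few words in two SAP sections and a check of the shells. No new data, analysis or table is needed.

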6.3.3.5 AE Severity

Adverse events will be graded on a 3-point scale and reported as indicated on the case report form (CRF). The intensity of an adverse experience will be graded as “Mild”, “Moderate”, and “Severe” using the criteria specified in Section 6.9 of the study protocol.

6.3.3.6 Relationship to the Investigational Medicinal Product

The relationship of an AE to dosing will be assessed as “Definite”, “Probable”, “Possible”, “Not Likely”, or Unrelated using the criteria specified in Section 6.9 of the study protocol.

6.3.3.7 AE with Irregular Start/End Dates

Partial dates may be imputed when appropriate. Imputed dates will be used to determine Study Day.

If a partial date is reported for the start of an AE, a complete date will be imputed by the following algorithm:

1. Only the year is reported: If the subject started receiving study medication in the previous year, then January 1 will be used as the starting date of the event. If the subject started receiving study medication in the year reported, then the date of the first dose of study medication will be used as the start of the event.
2. The month and year is reported: If the subject started receiving study medication prior to the month and year reported, then the first day of the month will be used as the starting date of the event. If the subject started receiving study medication during the month and year reported, then the date of the first dose of study medication will be used as the start of the event.

If a partial date is reported for the end of an adverse event and the adverse event is not continuing, a complete date will be imputed by the following algorithm:

1. Only the year is reported: If the subject started receiving study drug in the previous year, then the date of final study contact with the subject will be used as the end of the adverse event. If the subject started receiving study medication in the year reported, then the earlier of December 31 or the date of final study contact with the subject will be used as the end of the adverse event.
2. The month and year is reported: The earlier of the last date of the month or the date of final contact with the subject will be used as the end of the AE.

The above rules are subject to logical sense, for example, imputed start date should be on or prior to imputed end date.

All AEs will be included in the listings regardless the completeness of the onset dates.

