6.3.9 Concomitant Medications/Treatments

Concomitant medications administered at the time of randomization and during the study will be recorded on the CRF. The medication name, indication, dose, unit, frequency, route of administration, date(s) of administration and reason for administration will be recorded. This documentation should continue until discharge from the study.

A concomitant medication is any medication the subject enters the trial taking and is expected to continue taking for some portion of the trial, as well as any medication other than the investigational product that the subject takes during the course of the trial. All prescription and over-the-counter (OTC) medications (non-prescription drugs), including vitamins and herbal supplements, that subjects receive during the trial must be documented on the CRF. This documentation will continue until the subjects are discharged.

Concomitant medications will be coded using the World Health Organization Drug Dictionary (WHO-DD).

All prior and concomitant medication will be presented in individual subject data listings.

For medications with incomplete dates, imputation will be used to convert to a complete date. Imputed dates will be used to determine Study Day.

Partial medication start dates will be imputed as follows:

1. Only the year is reported: If the subject started to receive study drug in the year reported, then the date of the first dose of study drug will be used as the starting date of the medication. Otherwise, January 1 will be used as the start of the medication.
2. The month and year is reported: If the subject started to receive study drug during the month and year reported, then the date of first dose of study drug will be used as the starting date of the medication. Otherwise, the first day of the month will be used as the start of the medication.

Partial medication end dates will be imputed for non-ongoing medications as follows:

1. Only the year is reported: If the subject stopped to receive study drug in the year reported, then the date of the last dose of study drug will be used as the end date of the medication. Otherwise, December 31 will be used as the end of the medication.
2. The month and year is reported: If the subject stopped to receive study drug during the month and year reported, then the date of last dose of study drug will be used as the end date of the medication. Otherwise, the last day of the month will be used as the end of the medication.

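### The SAP's rule for partial adverse-event onset dates has no period anchor, so most month-only and nearly all year-only Period 2 onsets would be counted under the Period 1 treatment

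*SAP*

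**What the plan says.** SAP 6.3.3.7 gives the algorithm for incomplete onset dates.

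- Month and year known, dosing began in that month: "then the date of the first dose of study medication will be used as the start of the event".
- Month and year known, dosing began in an earlier month: "then the first day of the month will be used as the starting date of the event".
- Only the year known: the first-dose date if dosing began that year, or 1 January if it began the year before.

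The section says that partial dates may be imputed where appropriate and that imputed dates determine Study Day. It closes with a proviso that the rules must make sense, and its one example is that a start should not fall after an end. It does not mention period.

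SAP 6.3.3 allocates events by onset. "If the AE(s) onset date-time or date occurs after the first dose up until right before the first dose in the second treatment period", the event belongs to the first treatment period; an onset after the first Period 2 dose belongs to the second. SAP 8.4.1 then states: "The incidence of all TEAEs will be summarized by treatment".

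The SAP Introduction and SAP 3.1 give the calendar. Group 1 takes the combination first and digoxin alone second; its first Period 2 dose is on Day 19 and discharge is on Day 24. Group 2 takes digoxin alone first and the combination second; its first Period 2 dose (bexagliflozin) is on Day 15 and discharge is on Day 22.

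**The concern.** The imputation rule suits a parallel-group trial, where everything after the first dose belongs to one treatment. In a two-period crossover the first dose of study medication is always a Period 1 date. The SAP is period-aware elsewhere: SAP 6.3.3 names the first dose of the second period when it means that dose, and SAP 6.3.5 and 6.3.6 define baseline within each period.

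Moving an onset back to Day 1, or to the first of the month, will therefore often take a Period 2 event across the period boundary and put it under the other treatment. The by-treatment tables of treatment-emergent events are a central analysis of the secondary objective, the safety and tolerability of digoxin given with bexagliflozin (SAP 2.2).

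**Working it through.** The documents give no figure for this point, so there is none to reproduce. The check applies the SAP 6.3.3.7 rules and then the SAP 6.3.3 allocation to every possible case.

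**Inputs.** Period 2 clinic days on or after the first Period 2 dose: Days 19-24 in Group 1 (6 days) and Days 15-22 in Group 2 (8 days). Assumptions: Day 1 is equally likely to be any of the 365 dates of a non-leap year, and onset is equally likely on each of those clinic days.

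**Month-only onsets.** The imputed date is Day 1 or the 1st of the reported month. It falls in Period 2 only if the 1st of a month lies in the Period 2 window, on or before the true onset day. If the 1st falls on the j-th day of a window of k days, the k - j + 1 onset days from there on stay in Period 2. Summing over j gives k(k + 1)/2, and there are 12 month starts.

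- Group 1: 365 × 6 = 2190 cases; 12 × 21 = 252 stay; 2190 - 252 = 1938 go to Period 1, or 88.5%.
- Group 2: 365 × 8 = 2920 cases; 12 × 36 = 432 stay; 2920 - 432 = 2488 go to Period 1, or 85.2%.

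These figures count an imputed date equal to the first Period 2 dosing date as Period 2. SAP 6.3.3 requires an onset after that dose, and an imputed date has no time. If such ties go to Period 1 instead, the j = 1 terms drop out:

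- Group 1: 12 × (21 - 6) = 180 stay; 2010/2190 = 91.8% go to Period 1.
- Group 2: 12 × (36 - 8) = 336 stay; 2584/2920 = 88.5% go to Period 1.

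**Start dates for which every such event moves.** Counting ties as Period 2, these are the dates that leave no month start in the window.

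- Group 1: 365 - 12 × 6 = 293, or 80%.
- Group 2: 365 - 12 × 8 = 269, or 74%.

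**Year-only onsets.** Only 1 January can fall in the window.

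- Group 1: (2190 - 21)/2190 = 99.0%, or (2190 - 15)/2190 = 99.3% with ties in Period 1.
- Group 2: (2920 - 36)/2920 = 98.8%, or (2920 - 28)/2920 = 99.0%.

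**Reverse error.** Month-only onsets from Day 1 up to the day before the first Period 2 dose are never moved into Period 2: 0 of 365 × 18 = 6570 in Group 1, and 0 of 365 × 14 = 5110 in Group 2.

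**Examples, Group 1.**

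| Day 1 | First Period 2 dose | True onset | Imputed onset | Allocated to |
|---|---|---|---|---|
| 1 Aug | 19 Aug | 19-24 Aug | 1 Aug | Period 1 |
| 10 Aug | 28 Aug | 28-31 Aug | 10 Aug | Period 1 |
| 10 Aug | 28 Aug | 1-2 Sep | 1 Sep | Period 2 |
| 15 Aug | 2 Sep | 2-7 Sep | 1 Sep | Period 1 |

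**Sensitivity.** Protocol 6.7.4.2 requires monitoring for serious events for at least 14 days after discharge. Extending the onset windows by 14 days (Days 19-38 and Days 15-36) lowers the month-only share.

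- Group 1: 4780/7300 = 65.5%, or 5020/7300 = 68.8% with ties in Period 1.
- Group 2: 4994/8030 = 62.2%, or 5258/8030 = 65.5%.

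The year-only share stays near 97%.

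**Effect of one event.** With 18 subjects in both treatments, moving one subject's event lowers one incidence by 1/18 and raises the other by 1/18. The difference shifts by 2/18 = 11 percentage points, provided that the subject has no other qualifying event in either period.

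**The case against.** The case against has several parts, and much of it stands.

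- **The rule is not absolute.** Imputation is optional and made where appropriate, the closing proviso gives its start-before-end check only as an example, and the SAP Introduction calls the plan flexible guidance. A programmer could decline to backdate an event plainly recorded in Period 2. This lowers the risk but does not remove it: no period rule is written, and an onset moved back to Day 1 always passes the one check named.
- **The link to treatment is inferred.** SAP 6.3.3.7 names Study Day as the use of imputed dates, and SAP 6.3.3 allocates by onset without mentioning imputation. Reading the two together is natural, but it remains an inference.
- **The percentages are conditional on partial dates, which should be few.** Adverse events are assessed on every clinic day. Missing days are more likely in the out-of-clinic gap, and the rule leaves gap events correctly in Period 1.
- **The damage can be seen.** SAP 8.1 keeps the original value beside the imputed one, and SAP 6.3.3.7 lists every event. SAP 3.3 plans no hypothesis test.

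A reader might infer three stronger points that the documents do not support. First, that nearly all month-only Period 2 events are misplaced: the in-clinic share is 85-92%, and it falls to 62-69% when the 14 days after discharge are included. Second, that the rule favours or penalises bexagliflozin: the shift always runs from Period 2 to Period 1, but with 1:1 sequences (SAP 3.2) it runs in opposite treatment directions in the two groups, so no net bias is shown. Third, that the similar anchor for partial medication dates in SAP 6.3.9 does the same harm: the SAP only lists medications, and the table in Protocol 6.8 is not described as split by treatment, so no treatment allocation depends on those dates.

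**Conclusion.** The point holds. As written, the SAP's rules give the wrong treatment for most month-only onsets during the Period 2 clinic stay (for every one of them with roughly three quarters or more of start dates) and for nearly all year-only onsets. The result is a blurred by-treatment safety comparison rather than a bias in a known direction.

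The conclusion rests on reading SAP 6.3.3.7 together with SAP 6.3.3, on uniform start dates and onset days, and on literal use of the rule. The number of partial dates is not given. It should be small, so the expected impact is small and may be nil, although with 18 subjects even one moved event can be visible. The primary pharmacokinetic analysis is not affected. The correction is worth making because it is cheap.

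**What to change.** Add a period rule to SAP 6.3.3.7:

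1. Decide the period from what is available: the reported month or year, the end date, and the visit or date of recording where the CRF captures it.
2. If this shows that the event began on or after the first Period 2 dose, impute the later of that dose date and the first day of the reported month or year. State that an imputed onset equal to that dose date counts as Period 2, which settles the tie.
3. Events known to have started before that dose stay in Period 1. This includes events reported at Period 2 admission and events with onset in the out-of-clinic gap.
4. Where the period cannot be determined, for example a possible gap onset first recorded after Period 2 dosing, flag the event and show the by-treatment table under both allocations.

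In the first example above, step 2 gives the later of 19 August and 1 August, which is 19 August, so the event stays in Period 2.

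The cost is one paragraph of SAP text, a few lines of code, and review of a few ambiguous events before database lock. The annotated CRF is not among the documents, so whether it holds a recording date or visit for each event must be confirmed. If it does not, more events will fall under step 4.
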